The output of the pipelines are count data which are discrete, not continuous, and include only positive values. The counts,  $C_{ij}$ , are the observed number of microbes for the  $i^{th}$  sample and  $j^{th}$  feature where the features are the OTUs or microbial taxa. The data are normalized because library sizes (total counts for each sample, across all features) often have a large magnitude difference, which can cause a bias. The data are right skewed with, usually, a large number of data points having the value 0. Such data follows a Poisson distribution and therefore a Poisson regression model type (e.g. negative binomial model) will be used to investigate the relationship between microbiome and salt intake. For each feature, a model will be fitted with the feature as outcome and salt intake (a binary variable with two categories: treatment and placebo) as covariate. The differential count (fold change difference) between treatment and placebo will be estimated for each feature (OTU). To adjust for the multiple testing of several OTUs, a false discovery rate penalty will be applied and only fold changes with an adjusted p-value (Benjamini-Hochberg multiple test correction) smaller or equal to 0.05 will be considered statistically significant.

The analysis describes above using a Poisson regression model assumes the features (OTUs) are independent but it has been shown that microbial communities do interact in such way that changes in one feature affect another feature. However, the number of interactions can be large due to the number of features, and not easily fitted in a conventional regression model. Therefore, a machine learning algorithm (Random Forest or Neural Network) will be used to investigate the combined response of the features to salt intake. These algorithms can incorporate multiple and complex interactions between features without making an assumption about their distribution. The features will be used as predictor variables to predict salt intake (a binary variable with two categories: treatment and placebo). The results will be presented as the area under the curve (AUC) of a receiver operating curve (ROC) that reflect how well the features can predict treatment and placebo. Because these ensemble techniques do not assume the predictors

variable (OTUs) are independent, no multiple testing penalty is required but rather cross-validation will be undertaken.

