#### 9.4.3 Analysis of the Secondary Endpoint(s)

The secondary endpoints will be assessed independent of the results associated with the primary endpoints; secondary endpoints include blood pressure, whole blood epigenome, and whole blood and urine transcriptome. The effect of treatment and placebo will be investigated will be investigated for each secondary endpoint, as detailed below.

The association between blood pressure (systolic and diastolic) and salt intake will be assessed using multiple linear regression with salt intake (two categories: treatment and placebo) as the exposure variable and blood pressure outcome variable. The effect size, p-value and 95% confidence interval of the regression model will be provided as results.

The effect of salt intake on gene expression will be investigated in a differential expression analysis to identify genes whose expression differs significantly between treatment and placebo. The gene expression data will be normalized, using the weighted trimmed mean of M-values (TMM) method, an optimal method for the normalization of mRNA count data. Genes with an expression less than 1 Count Per Million (CPM = count/sum [counts] x 1million) in at least 2 samples will be excluded because results from genes with extremely low expression are not reliable. Gene expression is generated as count data which follows a Poisson distribution; therefore, a negative binomial model will be fitted using the R library *edgeR* developed to handle the specificities of mRNA sequencing data. The model computes likelihood ratio tests for the coefficients whilst taking into account dispersion. A deviance of goodness of fit test will be carried out to identify genes where the model fit was poor indicating that the dispersion estimate is away from the average dispersion. Dispersion outliers will not be considered for the results because the deviance indicates low quality or marked expression difference for the gene. Finally, genes with a log fold change not equal to 0 and a false discovery rate adjusted p-value  $\leq 0.05$  will be reported as significantly differentially expressed between treatment and placebo. Multiple testing correction, for the total number of genes considered, will be carried out using the Benjamini-Hochberg method.

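### The co-primary OTU analysis leaves a plain Poisson test open and gives the crossover no participant term; one route can inflate false positives, the other wastes power

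*Combined protocol and SAP*

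**What the plan says.** The microbiome is one of two primary endpoints. After describing the counts ("The data are right skewed with, usually, a large number of data points having the value 0"), section 9.4.2 states: "Such data follows a Poisson distribution and therefore a Poisson regression model type (e.g. negative binomial model) will be used". The model terms follow: "For each feature, a model will be fitted with the feature as outcome and salt intake" as a two-level covariate. No participant, period or sequence term is named, and no dispersion parameter, overdispersion check or software is given for this model. Significance is a Benjamini-Hochberg adjusted p-value of at most 0.05. The next paragraph refers back to the same analysis without mentioning the negative binomial: "The analysis describes above using a Poisson regression model assumes the features (OTUs) are independent".

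Section 9.4.3 treats RNA-seq, a secondary endpoint, more firmly. It starts from the same premise but commits: "Gene expression is generated as count data which follows a Poisson distribution; therefore, a negative binomial model will be fitted". It names edgeR and adds that "The model computes likelihood ratio tests for the coefficients whilst taking into account dispersion".

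Three other places bear on this. Section 9.4.1 promises in general terms to check assumptions and correct the procedure. Section 9.2 describes a mixed model with a random subject effect, but its list of outcomes omits the microbiome. Section 9 says there will be no formal SAP, so no later document is promised that would settle the choice.

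**The concern.** A Poisson model sets the variance equal to the mean. Its null hypothesis for an OTU is therefore stronger than equal means on salt and placebo: it also denies any variation between samples beyond counting noise. Microbial counts in one person vary from visit to visit for many reasons other than salt, and a Poisson test has nowhere to put that variation except the treatment contrast. A participant effect does not cure this, because the missing component is within the person. Benjamini-Hochberg does not cure it either, because it takes valid p-values as its input.

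The salt-only covariate list is a second gap, in the opposite direction. Each participant supplies a salt sample and a placebo sample. A model without a participant term puts the large differences between people into the error term and discards the advantage for which the crossover was chosen.

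At stake is whether a list of salt-responsive OTUs reported for a co-primary endpoint can be trusted, and whether real changes can be found.

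**Working it through.** **The plan's own figures.** None is given for the microbiome: no OTU mean, dispersion, number of OTUs, error rate or power. The only numerical calculation for a primary endpoint is for PWV. SD of the paired difference = 0.9 × √(2 × (1 − 0.3)) = 1.065 m/s. For a difference of 0.6 m/s, a two-sided paired t test at 0.05 has 80.5% power at n = 27 and 82.0% at n = 28, so the stated 28 reproduces. The addendum also reports 28 participants enrolled. N = 28 is used below; N = 40 gives nearly the same false-positive rates.

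**Plain Poisson, analytic.** Assume an unaffected OTU with mean μ and variance μ + φμ². The Poisson standard error is too small by the factor √(1 + μφ), so for independent samples the rejection rate at nominal 5% is

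2 × [1 − Φ(1.96 / √(1 + μφ))].

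Example: μ = 10, φ = 0.75 gives 1 + 7.5 = 8.5, √8.5 = 2.92, 1.96 / 2.92 = 0.67, and a rate of 50%. Simulation gives 49.7% at N = 28 and 50.7% at N = 40.

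| Mean μ | Rate at φ = 0.25 | Rate at φ = 2 |
|---|---|---|
| 1 | 8% | 26% |
| 10 | 30% | 67% |
| 50 | 59% | 85% |
| 100 | 70% | 89% |

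Within-person correlation lowers the rate. At μ = 10, φ = 0.75, N = 28 it falls to 43% at correlation 0.3 and 28% at 0.7.

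**After Benjamini-Hochberg** (200 unaffected OTUs assumed, N = 28). At μ = 10, φ = 0.75 the share flagged is 42%, 33% and 13% at correlations 0, 0.3 and 0.7. Over φ from 0.25 to 2 and the same correlations, it is 0.1% to 11% at μ = 1 and 43% to 89% at μ = 100.

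**Plain Poisson, simulated crossover with no salt effect.** Poisson-lognormal counts, N = 28, assumed between-person log-SD 1.0 and within-person log-SD 0.3 to 0.5:

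| Mean count | Rejection at nominal 5% |
|---|---|
| 1 | 8–12% |
| 5 | 19–33% |
| 50 | 58–67% |
| 500 | 81–93% |

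A version conditioned on each participant's total, which amounts to including a participant effect, gives 18–32%, 54–70% and 84–91% at means 5, 50 and 500. The participant effect therefore does not remove the problem. With a within-person log-SD of only 0.1 the rates are 6%, 17% and 56%.

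**Negative binomial with salt only.** On independent samples the likelihood ratio test rejects 4.7% to 6.3% of the time, as it should. On paired crossover data with no salt effect it rejects only 0–2%, because between-person variation inflates the error term. A paired test on within-person log ratios stays at 3–7%.

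For a true 1.5-fold change in the same setting, the salt-only negative binomial has 9–30% power at unadjusted 5%. The paired log-ratio test on the same data has 20–99%. The paired advantage is smallest for rare OTUs and largest for abundant ones.

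**The case against.** The strongest defence is that nobody intends a plain Poisson fit. The negative binomial is the only concrete model named in 9.4.2, and the word type points to a family. Section 9.4.3 moves from the same loose premise straight to a negative binomial. The later mention of a Poisson regression model introduces the discussion of OTU interactions and does not specify a second model. This stands as evidence of intent. A reader might infer that the plan's chosen test is a Poisson test; the documents do not support that. They only fail to exclude it.

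A reader might also infer that about half of unaffected OTUs would be declared salt-responsive. The documents do not support that figure either. It needs 1 + μφ of about 8.4, and no mean or dispersion is given. It also fits poorly with the plan's description of many zeros. In the simulated crossover, zeros make up about 15–17% of counts at mean 5, under 1% at 50 and none at 500. Where at least half the counts are zero (mean 1 or less), unadjusted rejection is about 0.4–12% and Benjamini-Hochberg flags under 1%. In assumed mixtures of 150 OTUs with 50–74% zeros, about 1 to 15 are falsely declared on average. That is a much smaller harm, but at least one false OTU still appears in 53–100% of such trials.

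The general promise in 9.4.1 to check assumptions also counts for the plan. It names no overdispersion check, criterion or fallback, however, and 9.4.2 states the doubtful assumption as fact.

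On pairing, 9.2 mentions a rank test on differences for the primary outcomes in general. It is not tied to OTU counts, and 9.4.2, the section specific to them, does not take it up.

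**Conclusion.** The concern holds in a conditional form. The Poisson statement is wrong for overdispersed counts, the model for a co-primary endpoint is not fixed, and the covariate list ignores the pairing.

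If plain Poisson is fitted, unadjusted false-positive rates run from slightly above nominal for rare OTUs (8–12% at mean 1) to 55–90% at means of 50 to 500. After Benjamini-Hochberg, the range over the assumed settings is 0.1% to 89%. If the negative binomial is fitted as described, false positives do not inflate, but the test is conservative and much power is lost.

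All means, dispersions, log-SDs, correlations and OTU numbers here are assumptions. The direction of each effect does not depend on their exact values; the size does. It would go too far to say that the trial will report dozens of false OTUs: that requires both a plain Poisson fit and mostly abundant OTUs, and the documents establish neither.

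**What to change.** In 9.4.2, delete the statement that the counts follow a Poisson distribution. Commit to one per-OTU analysis: either a negative binomial with estimated dispersion and participant and period terms, for example with the edgeR likelihood ratio test that 9.4.3 already names for RNA-seq, or a within-person log-ratio test. State that no significance claim will rest on a plain Poisson fit, with or without a participant effect. Quasi-likelihood tests are not named anywhere in the plan; if they are preferred, they should be introduced as new.

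For the negative binomial, also say how dispersion is estimated. With 28 participants and one sample per treatment there are 56 counts per OTU and 28 + 2 = 30 mean parameters (participants, treatment, period), which leaves 26 residual degrees of freedom.

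The cost is two sentences and slightly more analysis work. The software is already planned and no new data are needed.

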**Table 2: Specific activities by visit**

Activity	Visit 1 (baseline)	Visit 2 (after 2-week treatment)	Visit 3 (after 3-week washout)	Visit 4 (after second 2-week treatment)
24-Hour nutrient recall	x	x	x	x

Psychophysical Taste Task: Sucrose and Salt Detection Thresholds	x	x	x	x
Psychophysical Taste Task: Sucrose and Salt Preference	x	x	x	x
History and physical exam with medication history	x	x	x	x
Baeke's physical activity questionnaire	x			
Pittsburg sleep questionnaire	x			
Stool/skin/mouth swabs for microbiome analysis	x	x	x	x
Urine sample	x	x	x	x
Blood sample	x	x	x	x
Vascular function	x	x	x	x
24-hour blood pressure monitor given to participant	x		x	
24-hour blood pressure monitor returned by participant		x		x

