safe, intake in various cultures around the world. The increment in salt intake beyond the participant's usual diet is equivalent to eating 1-2 bowls of soup and is a dose commonly administered to treat orthostatic hypotension in patients who suffer from this disorder. It should be noted that the protocol focuses on normotensive volunteers and excludes patients with hypertension or heart failure for whom a transient increase in dietary sodium could pose a risk. We will assess, gut, skin and saliva microbiome. The oral cavity is an excellent source of easy-to-access biological material for studies of oral microbiome. This is due to the quick, non-invasive and low-cost collection. The most used source of oral samples is saliva (collected by passive drool or spit). The collection of the skin microbiome samples is commonly performed using the swabbing method. The sampling for skin microbiome was guided by the aim to consider two of the three skin microenvironments types: Sebaceous and moist microenvironments. For the first, the Retroarticular Crease was chosen and for the latter, the Antecubital Fossa was selected. These sites provide also the advantage of being relatively less exposed than dry sites such as the forearm and hence less likely to have the external environment microbiome over-represented.

The oral samples are not collected to investigate gut microbiome but rather to evaluate changes in oral microbiome with respect to changes in sodium intake. The aim is to find out if changes in sodium intake are correlated with microbiome changes in the oral cavity, in the gut and on the skin. Each site is considered separately first and then patterns of changes between sites are considered.

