7. Psychophysical Taste Task: Sucrose and Salt Preference: Sucrose and salt preference will be assessed using a two-series paired comparison-tracking method developed at the Monell Center for Adults. Subjects will be presented with pairs of solutions differing in sucrose concentration (3, 6, 12, 24, and 36 g per 100 mL) and salt (0.92–6.14% wt/vol NaCl). They will be asked to taste the solutions without swallowing and point to which of the pair they liked better. Subsequently, each pair presented will be determined by the subject's preceding preference choice. The entire task is then repeated with the stimulus pairs presented in reverse order. After completion of the taste task, the geometric mean of the sucrose concentrations chosen will be determined. This serves as an estimate of the participant's most preferred level of sucrose. The task takes approximately 15 minutes to complete.

8. Baecke's Physical Activity Questionnaire: Physical activity will be assessed using 16 questions involving three habitual physical activities (occupational physical activity, physical exercise, and leisure activities) during the previous 12 months.

9. Pittsburgh Sleep Quality Index (PSQI): This is a 19-item self-rated questionnaire for evaluating subjective sleep quality over the previous month.

10. Microbiome: Skin, saliva and stool samples will be collected by the GENE-FORECAST-SIT staff based on the utilization of Norgen kits. Participant will be swabbed in three locations of the skin and will spit in a prepared vial. Subjects will be required to not shower within 12 hours of sampling based on the guidelines from the NIH common fund Human Microbiome Project, an initiative to generate resources and facilitate the characterization of the human microbiota (Human Microbiome Project, *Nature*, 2012). Stool kits will be previously mailed to participant for collection and participant will give stool sample to GENE-FORECAST-SIT staff at the clinic appointment.

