**Microbiome:**

BODY SITE	SPECIMEN	COLLECTION TUBE
Oral Cavity	Saliva	Saliva DNA Collection, Preservation, and Isolation Kit
Skin	Retroauricular Crease (Left)	Swab Collection and DNA System
	Retroauricular Crease (Right)	
	Antecubital Fossa (Left)	
	Antecubital Fossa (Right)	
GI Tract	Stool	Norgen Stool Nucleic Acid Collection and Preservation System

Total volume of blood collected per visit = 87 ml, which is equivalent to about 5.8-6 tablespoons of blood.

Biological specimens collected from individuals will include peripheral venous blood and urine samples collected by phlebotomy. Oral microbiome samples will be acquired using a spit collection kit. Skin swabs will be used to obtain skin microbiome samples from the left and

right retroarticular crease, as well as, the left and right antecubital fossa. Stool microbiome samples will be collected in a stool kit mailed to participants prior to clinic visit. Detailed instructions for the preparation, handling, storage, and shipment of specimens will be explained in the study's MOP.

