#### 9.4.2 Analysis of the Primary Endpoints

The two primary endpoints are vascular function and microbiome.

First, vascular function difference between placebo and treatment (salt intake) will be estimated. Then, microbiome differential between treatment and placebo will be identified and estimate for each of the microbiome collection sides (skin, oral and gut). Details of the vascular function and microbiome analyses with respect to treatment and placebo are provided below.

Vascular function (e.g. pulse wave velocity, PWV) will be first analyzed as a continuous variable. Its relationship with salt intake will be investigated through multiple linear regression with vascular function as outcome and salt intake (a binary variable with two categories:

treatment and placebo) as exposure variable. For this analysis only samples with complete data for vascular function and salt intake will be considered. The outcome variable will be log transformed if it departs markedly from the Gaussian distribution. The aim of this first analysis is to estimate the effect of salt intake on vascular function. The effect size, p-value and 95% confidence interval will be provided as results.

The second endpoint is microbiome; the microbiome data of each of the all the collection sites (oral, gut and skins) will be analyzed separately. Prior to investigating the relationship between microbiome and salt intake, the raw microbiome data requires extensive processing and quality controls (QC) because of challenges posed by this type of data and the potential of spurious results if appropriate QC are not applied. The raw data will be processed in mainly 5 steps: (a) reads preparation (assembly of paired reads, filtering of low quality reads and identification of unique sequences), (b) Operational Taxonomic Units - OTU clustering (selection of unique OTU sequences), (c) quality controls (identification and removal of artifacts from amplicon reads, in OUT sequences). These tasks will be carried out using pipelines included in the standards operating protocols (SOPs) developed and used by the NIH Human Microbiome Project. For the metagenomic microbiome data, the *HUMANN2* pipeline will be used and for the 16s microbiome data the *DADA2* pipeline will be used.

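### The plan has no rule for four skin swabs per participant-visit and its OTU model has no participant, visit or location term, so skin p-values are not valid, in a direction the documents cannot settle

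*Combined protocol and SAP*

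**What the plan says.** - **Specimens.** The microbiome table in Section 8.2.2 lists four skin specimens, starting with "Retroauricular Crease (Left") and its right-hand pair, then the left and right antecubital fossa. The table is repeated in Section 8.2.4.4. The text below the Section 8.2.2 table agrees: "Skin swabs will be used to obtain skin microbiome samples from the left and" right sides of both locations.
- **Conflicting count.** Section 8.2, item 10, says "Participant will be swabbed in three locations of the skin and will spit in a prepared vial".
- **Visits.** Table 2 has the row "Stool/skin/mouth swabs for microbiome analysis" marked at all four visits.
- **Why these locations.** Section 4.2 chose them to cover two kinds of skin environment: "Sebaceous and moist microenvironments".
- **Grouping.** Section 9.4.2 says the "collection sites (oral, gut and skins) will be analyzed separately". Skin is therefore one site of three.
- **Model.** In Section 9.4.2 the counts "are the observed number of microbes for the" i-th sample and j-th feature. Then "For each feature, a model will be fitted with the feature as outcome and salt intake" (treatment or placebo) as covariate. No term for participant, visit, period, location or side is given. A feature is significant when its Benjamini-Hochberg adjusted p-value is at most 0.05.
- **Elsewhere.** The mixed model with a subject random effect in Section 9.2 names blood pressure, ambulatory pressure, biochemical markers, vascular function, transcriptome and epigenome. It does not name the microbiome.

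**The concern.** Read as written, the two end-of-period visits of 28 participants give 28 × 2 × 4 = 224 skin samples, but only 28 × 2 = 56 participant-visits. Treatment is assigned to a participant for a period, so the four swabs from one visit are replicate readings of one treated unit. A per-sample model with salt as its only term makes two errors that pull in opposite directions. It counts same-visit swabs as independent, which shrinks the p-value. It also leaves stable differences between participants, and between crease and fossa, in the error term, which inflates the p-value.

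Benjamini-Hochberg needs valid input p-values to hold its 5% false discovery rate. If they are too small, false skin findings are reported on a primary endpoint. If they are too large, real changes are missed. Pooling the two environments without a location term also blurs the contrast the sampling was chosen to cover.

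**Working it through.** **Plan's own figure.** There is none for this point: the documents give no sample size, variance or correlation for any microbiome feature. The only power figure with all its inputs is for pulse wave velocity (difference 0.6 m/s, SD 0.9, correlation 0.3, 28 participants). There the SD of the difference is 0.9 × √(2 × 0.7) = 1.065. A paired t-test then needs 27 participants (80.5% power) and has 82.0% at 28, close to the stated 28. This says nothing about skin.

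**Inputs.** Four swabs per visit (Section 8.2.2); two end-of-period visits, 2 and 4 (Table 2); 28 participants (addendum); two-sided 5% (Section 9.2). The following are assumptions. On the log scale, random variance is split into participant p, participant-by-visit v and swab s, with p + v + s = 1. A fixed crease-versus-fossa difference adds location variance L, expressed relative to that total.

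**Formulas.** Per participant, the salt mean minus the placebo mean has true variance 2(v + s/4) = (4v + s)/2.

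- Salt-only model: it assumes 2(p + v + s + L)/4 = (p + v + s + L)/2. The ratio of true to assumed variance is R1 = (4v + s)/(p + v + s + L), which exceeds 1 only if 3v > p + L.
- Participant effect added, swabs still separate rows: two visit values repeated four times each contribute 4v to the within-participant sum of squares, and location contributes 8L, on 7 degrees of freedom. The residual mean square estimates s + 4v/7 + 8L/7. So R2 = (4v + s)/(s + 4v/7 + 8L/7), which exceeds 1 if 3v > L.
- True false-positive rate of a nominal 5% test = 2[1 − Φ(1.96/√R)].

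Example with p, v, s = 0.4, 0.2, 0.4 and L = 0: R1 = 1.2/1 = 1.20, giving 7.4%. R2 = 1.2/(0.4 + 0.114) = 2.33, giving 19.9%.

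**Results.** The first rate is from the formula. The figure in brackets, and the last column, are from 20,000 simulated null Gaussian trials per row.

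| p, v, s | L | R1 | Salt only | R2 | Participant effect only | One value per visit, paired |
|---|---|---|---|---|---|---|
| 0.4, 0.2, 0.4 | 0 | 1.20 | 7.4% (7.7%) | 2.33 | 19.9% (20.1%) | 4.9% |
| 0.4, 0.2, 0.4 | 1 | 0.60 | 1.1% (1.2%) | 0.72 | 2.1% (2.1%) | 4.9% |
| 0.3, 0.3, 0.4 | 0 | 1.60 | 12.1% (12.9%) | 2.80 | 24.1% (24.4%) | 5.1% |
| 0.3, 0.3, 0.4 | 0.5 | 1.07 | 5.8% (5.9%) | 1.40 | 9.8% (9.6%) | 5.0% |
| 0.3, 0.3, 0.4 | 1 | 0.80 | 2.8% (2.8%) | 0.93 | 4.2% (4.2%) | 5.1% |
| 0.2, 0.3, 0.5 | 0 | 1.70 | 13.3% (13.9%) | 2.53 | 21.8% (22.4%) | 5.1% |
| 0.5, 0.1, 0.4 | 0 | 0.80 | 2.8% (3.2%) | 1.75 | 13.8% (14.0%) | 5.1% |
| 0.5, 0.05, 0.45 | 0 | 0.65 | 1.5% (1.7%) | 1.36 | 9.3% (9.3%) | 4.8% |
| 0.5, 0, 0.5 | 0 | 0.50 | 0.6% (0.7%) | 1.00 | 5.0% (4.9%) | 4.9% |
| 0.5, 0, 0.5 | 1 | 0.25 | 0.0% (0.0%) | 0.30 | 0.0% (0.0%) | 4.9% |

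**Count data.** Negative binomial simulations in 13 other assumed settings (28 participants, 400 to 500 runs each) gave 2.8% to 28.0% for the salt-only model and 2.8% to 22.8% with a participant effect. With the four swabs summed and paired by participant, the rate was 3.2% to 7.7%, with simulation error of about 2 points. The participant effect raised the rate in some settings (4.8% to 9.4%) and lowered it in others (28.0% to 20.0%; 15.2% to 9.0%).

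**The case against.** The strongest reply is that separate entry of the swabs is inferred. Section 9.4.2 speaks of a sample without defining it, handling details are left to the Manual of Operations, and Section 8.2 counts three skin locations. If the swabs are pooled, or each location and side is analysed alone, the four-fold replication disappears. That is true, but no text in the protocol says so. The statement in Section 4.2 that each site is first considered on its own refers, in context, to mouth, gut and skin. Even with pooled swabs, the salt-only model would still ignore the crossover pairing.

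The plan also has partial cover. Section 9.2 tests primary outcomes on differences, which implies one value per person, and Section 9.4.1 promises to check assumptions and correct the procedure. Neither says how four swabs become one value.

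Two stronger readings are tempting, and the documents support neither.

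- A reader might infer that skin p-values are simply too small. That requires 3v > p + L, and the documents give none of these quantities. A crease-versus-fossa difference alone can turn an inflated rate into a conservative one: 12.9% becomes 2.8% in the table.
- A reader might infer that adding a participant effect always makes matters worse. The plan proposes no such effect for OTUs. With no visit variance and no location difference it restores 5%, and in the count simulations it moved the rate either way.

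**Conclusion.** The point stands in this form: the plan lists four skin swabs per participant-visit, gives no rule for combining them, and fits a per-sample model without participant, visit or location terms. Followed as written, it does not control the error rate of the skin OTU tests. In the Gaussian settings tried, a nominal 5% test ran from about 0% to 14%. A participant effect alone gave about 0% to 25%; it is right by construction only when both v and L are zero, and otherwise only by coincidence, at 3v = L. The count simulations, with other assumed variances, reached 28.0% and 22.8%.

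All variance shares and location differences are assumptions, so these ranges show how far the rate can move and do not predict it. The direction is unknown. The need for a rule does not depend on them, because the paired analysis of one value per visit stayed at 4.8% to 5.2% in every Gaussian setting. The ranges do assume that swabs enter as separate samples.

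**What to change.** In Section 9.4.2, state for skin:

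- Combine left and right swabs into one value per participant-visit within each microenvironment (for example, sum reads after normalisation).
- Analyse retroauricular crease and antecubital fossa separately.
- Compare treatment with placebo within participant, using the end-of-period visits and a participant effect.
- If swabs are to stay as separate rows instead, include location plus participant and participant-by-visit random effects. A participant effect alone should not be accepted.

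Reconcile the three skin locations in Section 8.2, item 10, with the four specimens in the tables of Sections 8.2.2 and 8.2.4.4.

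The cost is analysis wording, with no new samples or visits. The downside is one extra skin family in the multiplicity count.
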